## 6.5 PK Analyses

All PK analyses will be conducted based on the PK Population. All PK data listings will be presented based on the Safety Population.

PK concentration data will be summarized by study day and nominal time. The trough concentrations will be summarized by study day. The summary statistics for concentration data will include n, arithmetic mean, SD, median, minimum, maximum, and coefficient of variation (CV%).

PK parameters in **Table 3** will be summarized by study day. Summary of  $t_{max}$  will include n, median, minimum, and maximum only. For other PK parameters, n, arithmetic mean, SD, median, minimum, maximum, coefficient of variation (CV%), geometric mean, and geometric CV% will be presented.

The CV% is computed as:

$$CV\% = 100 \times (SD/Mean).$$

The geometric mean is computed as:

$$\text{Geometric mean} = \exp(\text{arithmetic mean of log transformed data}).$$

The geometric CV% is computed as:

$$CV\% \text{ geometric mean} = (\text{sqrt}(\exp(\text{variance for log transformed data}) - 1)) \times 100.$$

Individual as well as arithmetic mean concentration-time profile plots for serum concentration and trough concentrations will be presented in linear and semi-logarithmic scale.

The scatter plots of individual and geometric mean values for  $AUC_{0-12h}$  and  $C_{max}$  for ciprofloxacin and doxycycline will be presented for single dose and steady state profiles. The scatter plots of individual and geometric mean values for the ratio of  $AUC_{0-12h}$  and  $C_{max}$  will be presented for single dose and steady state profiles.

### 6.5.1 Equivalence Testing for Primary PK Endpoints

For each of the two antibiotics, the goal with the primary PK endpoint is to demonstrate that vaccination with AV7909 does not affect the steady-state PK profile. The equivalence testing will be constructed using paired two one-sided t-tests (TOST) to provide the point estimate and 90% CIs for geometric mean of the within-participant ratios of the steady-state values of  $AUC_{0-12h}$  and  $C_{max}$  post two doses of AV7909 (Day 35 for ciprofloxacin and Day 38 for doxycycline) vs. pre-vaccination of AV7909 (Day 8 for ciprofloxacin and doxycycline). The analyses will be conducted with natural log transformation of PK parameters. Results obtained from transformed analyses will be back-transformed by exponentiation for presentation. To conclude that AV7909 vaccine has no effect on the steady-state PK of ciprofloxacin or doxycycline, the 90% CIs should fall entirely within the equivalence range of [0.80, 1.25] for both  $AUC_{0-12h}$  and  $C_{max}$ .

### 6.5.2 Equivalence Testing for Secondary PK Endpoints

For each antibiotic, the secondary PK analyses will be performed to evaluate the effect of vaccination with AV7909 on the single-dose PK profile. The equivalence tests will be conducted in the similar statistical manner as the primary analyses. If the 90% CIs for geometric mean of the within-participant ratios of the single-dose values of  $AUC_{0-12h}$  and  $C_{max}$  post two doses of AV7909 (Day 31 for ciprofloxacin and Day 32 for doxycycline) vs. pre-vaccination of AV7909 (Day 4 for ciprofloxacin and Day 2 for doxycycline) fall entirely within the equivalence range of [0.80, 1.25] for both  $AUC_{0-12h}$  and  $C_{max}$ , it is concluded that AV7909 vaccine has no effect on the single-dose PK for ciprofloxacin or doxycycline.

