Antibiotic PK: Assessment of the effect of vaccination with AV7909 on the PK of either antibiotic will be made using the geometric mean of the within-participant ratio of C_{\max} and AUC_{0-12h} for either ciprofloxacin or doxycycline before (Day 8) vs after (Day 35 or Day 38) AV7909 vaccination. The equivalence (no interaction) margin for the ratio is [0.80, 1.25], which will be compared with the 90% CI for the geometric mean ratio. Assuming that the coefficient of variation (CV) with the within-participant ratio is 30% and the true ratio is 0.95, 27 participants allows for 90% power at significance level 0.05 while 34 participants would provide 95% power. A group size of 40 participants in each of the antibiotic PK groups (Group 1A and Group 2A) is planned to allow for up to 30% participants being excluded from the PK population.

Immunogenicity: Sample sizes of 53 in each cohort (AV7909 alone vs AV7909 + antibiotic [either ciprofloxacin or doxycycline]) provide 90% power at the 2.5% one-sided significance level for the non-inferiority test (defined as the lower bound of the two-sided 95% CI of the ratio greater than 0.5), if the true ratio of geometric means is 0.85 and the CV of NF_{50} values between participants in the same group is 100%. A cohort size of 70 is planned to allow for up to 25% of participants to be excluded from the immunogenicity population.

AV7909 Anthrax Vaccine

IND 014451

Protocol EBS.AVA.210, Version 3.0 (28 October 2019)

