4.3.3. Doxycycline

The doxycycline dose (100 mg), dosing schedule [twice a day (q 12 hr)] and route of administration [by mouth (po)] being used in this study are those that would be used for PEP in the event of inhalation exposure to anthrax. As with ciprofloxacin, doxycycline administration will occur on an intermittent daily rather than a continuous daily dosing schedule for the same reason this approach is used for ciprofloxacin. This schedule will provide the required single dose and steady state PK dosing regimens needed and, in addition to achieving the needed steady-state concentrations before and after vaccination, is designed to achieve the immunogenicity end-points while restricting the antibiotics administered to the minimum required to achieve these ends.

However, since the half-life of doxycycline is considerably longer than that of ciprofloxacin (15-16 hours after a single dose and 22 or more hours after multiple doses compared to 3-7 hours for ciprofloxacin), participants in Group 2 will receive a few more doses of antibiotic than those in Group 1. This is because we believe more days of dosing will be required to achieve steady state. Thus, Group 2 will receive seven days of dosing with doxycycline compared to five days used for ciprofloxacin before tests for steady state are applied.

Doxycycline will also be administered in three courses that will be used both by site staff for in-clinic visits and by participants when they are at home. The format of the courses in terms of number of tablets and when participants will receive each course will be described in the Pharmacy Manual.

The doxycycline dosing periods were chosen because they have been shown to have an effect on humoral immunity in mice {Woo et al, 1999} and to affect post-vaccination cell-mediated immunity in swine {Pomorska-Mól et al. 2014}, suggesting it could also affect the antibody response to AV7909. The intermittent dosing schedule was chosen in the hopes of minimizing any adverse effects from doxycycline.

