10.5.1.3. Equivalence Testing for Secondary PK Endpoints

The secondary PK analyses will be performed to evaluate the effect of vaccination with AV7909 on the single-dose PK profile for either ciprofloxacin or doxycycline. The equivalence tests will be conducted in a similar statistical manner as the primary analyses. If the 90% CIs for geometric mean of the within-participant ratios of the single-dose values of AUC_{0-12h} and C_{max} post two doses of AV7909 (Day 31 for ciprofloxacin and Day 32 for doxycycline) vs. pre-vaccination of AV7909 (Day 4 for ciprofloxacin and Day 2 for doxycycline) fall entirely within the equivalence range of [0.80, 1.25] for both endpoints, AUC_{0-12h} and C_{max}, it will be concluded that the AV7909 vaccine has no effect on the single dose PK for ciprofloxacin or doxycycline.

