## 2.4 Sample Size and Power Considerations

The sample size for this study was selected based on both the primary and secondary endpoints.

Assessment as to whether vaccination with AV7909 affects the PK of either ciprofloxacin or doxycycline will be made based on the geometric mean of the within-participant ratios (post-vaccination over pre-vaccination) of AUC0-12h and Cmax. The equivalence margin for the geometric mean ratio is [0.80, 1.25], which will be compared with the 90% confidence interval (CI) for the geometric mean of with-participant ratios of AUC0-12h and Cmax. Assuming the coefficient of variation (CV) is 30% for the geometric mean ratio and the true geometric mean ratio is 0.95, 27 participants allow for 90% power to reject the null hypothesis at a significance level of 5%. A group size of 40 participants for Group 1A (AV7909 + ciprofloxacin with PK) or Group 2A (AV7909 + doxycycline with PK) is planned to allow for up to 30% of participants being excluded from the PK Population.

A sample size of 53 in each of the IP groups (Group 1 = AV7909 + ciprofloxacin, Group 2 = AV7909 + doxycycline, and Group 3 = AV7909 only) provides 90% power at 2.5% one-sided significance level for the non-inferiority test, defined as the lower bound of the two-sided 95% CI of the geometric mean ratio of the AV7909 + antibiotic over AV7909 only (Group 1 vs. Group 3, Group 2 vs. Group 3) greater than 0.5. This assumes that the true ratio of the geometric means between two groups is 0.85 and the CV of TNA NF50 values in each group is 100%. A total of 70 per IP group is planned to allow for up to 25% of drop-out rate.

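### For doxycycline, the single-dose rule concludes more than its two metrics can show: AUC0-12h and Cmax barely respond to a change in clearance when the half-life is 15-16 h

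*SAP*

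**What the plan says.** SAP 6.5.2 compares single-dose doxycycline PK after vaccination (Day 32) with that before it (Day 2), using two metrics: AUC0-12h and Cmax. The 90% CIs of the geometric mean ratios must "fall entirely within the equivalence range of [0.80, 1.25] for both" metrics. Where that condition is met, the section draws this inference: "it is concluded that AV7909 vaccine has no effect on the single-dose PK for ciprofloxacin or doxycycline". Protocol 10.5.1.3 has the same rule and ends: "it will be concluded that the AV7909 vaccine has no effect on the single dose PK for ciprofloxacin or doxycycline".

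The method carries over from the primary test in SAP 6.5.1: paired two one-sided t-tests on the natural-log scale. SAP 2.2.2 puts the last sample of each PK session at 12 h. Protocol 4.3.3 gives the doxycycline half-life as "15-16 hours after a single dose and 22 or more hours after multiple doses compared to 3-7 hours for ciprofloxacin".

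SAP 2.3.2.2 and 4.8, and protocol 10.1.2.2 and 10.8, place the single-dose comparison outside formal testing and report it for information only.

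**The concern.** The conclusion is about single-dose PK as a whole, but the evidence for doxycycline covers less than one half-life. Early concentrations after one dose are governed mainly by how much drug is absorbed, how fast, and into what volume. Clearance acts mostly on the part of the curve after 12 h, which AUC0-12h does not see. Cmax is less sensitive still.

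At steady state the position differs: AUC0-12h over a dosing interval equals bioavailable dose divided by clearance, so it carries almost the whole of a clearance change. The same limits are therefore applied to two quantities of very different sensitivity. The study report could state an effect at steady state and none after a single dose, with the difference due to the metric alone.

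**Working it through.** **Inputs from the documents**
- Limits 0.80 to 1.25 on both metrics (SAP 6.5.2); paired TOST, 5% per one-sided test, log scale (SAP 6.5.1).
- Variability: "Assuming that the coefficient of variation (CV) with the within-participant ratio is 30% and the true ratio is 0.95" (protocol synopsis).
- n = 27 for 90% power (SAP 2.4) and n = 34 for 95% (protocol synopsis). Forty less the 30% exclusion allowance leaves 28.
- Half-life 15-16 h after a single dose (protocol 4.3.3); last sample at 12 h (SAP 2.2.2).

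**Assumptions (not in the documents):** one-compartment oral model, absorption rate ka from 0.5/h to near-instant, volume and bioavailability unchanged, and the same CV for Cmax as for AUC0-12h.

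**1. Reproduce the plan's figures.** SD of the log ratio = sqrt(ln(1 + 0.30²)) = 0.2936. Exact paired TOST power at a true ratio of 0.95 is 0.905 at n = 27 and 0.955 at n = 34. Both stated sample sizes reproduce. At a true ratio of 1.25 the pass probability is 5.0%.

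**2. Share of exposure inside 12 h.** With k = ln 2 / half-life, per unit of bioavailable dose over volume:

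AUC0-12h = ka/(ka − k) × [(1 − e^(−12k))/k − (1 − e^(−12ka))/ka], and AUC0-inf = 1/k.

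At 15.5 h and ka = 1/h, k = 0.04472. AUC0-12h = 1.0468 × (9.2865 − 1.0000) = 8.674 and AUC0-inf = 22.36, so the window holds 8.674/22.36 = 39%. Over the whole range it holds 35-43%.

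**3. Cut clearance by 20%, so that AUC0-inf rises by 25%.** Now k = 0.8 × 0.04472 = 0.03578. AUC0-inf = 27.95 (ratio 1.25), but AUC0-12h = 1.0371 × (9.7564 − 1.0000) = 9.081, a ratio of 9.081/8.674 = 1.047. For Cmax, tmax = ln(ka/k)/(ka − k) and Cmax = e^(−k·tmax): 0.8646 before and 0.8838 after, a ratio of 1.022. Over the whole range the AUC0-12h ratio is 1.043-1.052 and the Cmax ratio 1.00-1.035.

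**4. Probability of passing with that clearance change**

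| Evaluable n | AUC0-12h alone (whole range) | Full rule with Cmax (15.5 h, ka = 1/h, correlation 0 to 0.95) |
|---|---|---|
| 27 | 0.906-0.929 | 0.88-0.91 |
| 28 | 0.916-0.937 | 0.90-0.92 |
| 40 | 0.977-0.986 | 0.98 |

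Doubling AUC0-inf through clearance gives an AUC0-12h ratio of only 1.12-1.13, and AUC0-12h then passes 55-58% of the time at n = 27 (15.5 h, ka 1-2/h).

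**5. The same change in the primary comparison.** The Day 38 morning dose is the 13th of its course (12 on Days 32-37, plus one). By superposition, AUC over that interval equals single-dose AUC from 0 to 13 × 12 = 156 h. The ratio is 1.246-1.247 at a half-life of 15-16 h and 1.234 at 22 h, which passes 5.5-5.6% and 7.7% of the time at n = 27.

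**The case against.** The strongest reply is that nothing depends on this sentence. The single-dose comparison is descriptive, and the immunogenicity test is gated on the steady-state result only. A clearance change of this size would fail the primary test more than 92% of the time. That stands, and it sets the severity. It does not make the sentence supportable: both sections still contain a pass rule and a stated conclusion, which can go straight into the study report.

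A second reply is that the phrase is shorthand, since AUC0-12h and Cmax are named in the same sentence and the hypotheses concern only those two. This is fair, and it is why narrowing the words is enough.

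A third is model dependence. The one-compartment form, ka and the fixed volume are assumptions. A linear one-compartment model also cannot give both 15-16 h after one dose and 22 h or more after repeated dosing, and nothing in the documents points to a clearance-only effect of vaccination. The exact ranges should therefore be read loosely. The direction is robust: the result hardly changes with ka, and a longer half-life makes the metric less sensitive.

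A reader might infer an inflated type I error, with passes above 90% where 5% was intended. The documents do not support that. The SAP's null is on AUC0-12h and Cmax, and for that null the error stays at 5%. The high pass rate arises only when the result is read as a statement about total exposure and the whole change comes through clearance. A 25% change in bioavailability moves AUC0-12h by the full 25% and passes 5% of the time.

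**Conclusion.** The point holds as a mismatch between conclusion and metric, confined to the doxycycline single-dose statement in SAP 6.5.2 and protocol 10.5.1.3. Given the documents' half-life, CV, limits and sample size and the assumed model, a clearance change worth 25% of total exposure passes the full rule about 90% of the time at n = 27-28, against about 5-8% for the primary steady-state comparison. Severity is low: the comparison is for information only and the primary conclusion is unaffected.

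Two further inferences should be resisted. The synopsis does not share the fault; it asks only whether the named single-dose values are affected. Nor does steady-state AUC0-12h isolate elimination: it reflects clearance and bioavailability together.

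**What to change.** In SAP 6.5.2 and protocol 10.5.1.3 only, word the doxycycline conclusion as no effect on single-dose Cmax and on exposure over the first 12 h, in place of no effect on single-dose PK. Add one sentence saying that a change in overall exposure through clearance is assessed primarily by steady-state AUC0-12h, Day 38 against Day 8. Keep every planned ratio and 90% CI. The synopsis needs no change.

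Putting AUC0-inf into the rule would not be a clean repair. It is derived on single-dose days, but 57-65% of it lies beyond the last sample and would be extrapolated from less than one half-life of data.

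The cost is two edited sentences and a narrower single-dose claim for doxycycline. No samples, analyses or programming change.

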### 6.5.3 Time to Steady State Assessment Using Trough Concentrations

To evaluate time to steady state before and after AV7909 vaccination, the trough levels of ciprofloxacin will be analyzed by comparing values on Days 4, 5, 6, 7, and 8 and on Days 31, 32, 33, 34 and 35; the trough levels of doxycycline will be analyzed by comparing values on Days 2, 3, 4, 5, 6, 7, and 8 and on Days 32, 33, 34, 35, 36, 37 and 38.

Stepwise testing for linear trend, the application of the NOSTASOT (No Statistical Significance Of Trend) methodology to trough concentrations proposed by [Maganit et al., 2008](#) involves straight line approximations to the aggregate plasma concentration curve over specified time intervals; therefore, the null hypothesis is that there is no linear trend, i.e., the slope of the regression line equals zero. The alternative is that there is a linear trend (slope not equal to zero). The first linear contrast uses the entire range of time points included in the model. If the contrast is significantly different from zero at  $\alpha=0.05$ , a new linear contrast is tested, this time excluding the earliest time point. This testing continues, based on contrasts successively excluding the next earliest time point from the start of the study, until the contrast is no longer significantly different from zero or until only three timepoints remain in the contrast. If the final contrast is not statistically significant, then the first timepoint included in that contrast is considered to be the time point at which steady state is attained. If the final contrast includes three timepoints and is still statistically significant, then steady state is considered not to have been attained by the end of the study.

The repeated measures ANOVA model will be conducted with natural log transformed trough level as response and study day as fixed factor. The slope estimates along with the 90% confidence intervals for the slope will be presented as results.

## 7 IMMUNOGENICITY ANALYSIS

All the immunogenicity analyses presented in the tabulations and figures will be performed based on the Immunogenicity Population as defined in [Section 3.2](#). The immunogenicity data listing will be presented based on the Safety Population.

Immunogenicity is assessed with TNA NF50. In the tabulations and figure, the non-missing TNA NF50 values which are below the LLOQ will be imputed with 0.032, which is ½ the LLOQ of the assay ([BBRC Study Report 762-G004690](#)). In the data listing, TNA NF50 values which are below the LLOQ will be presented in the original values.

### 7.1 Summary of Immunogenicity Data

The summary of immunogenicity response TNA NF50 at Day 37 and IP group (Group 1, 2, 3, and Total) will include:

- Descriptive summaries (n, mean, median, standard deviation, minimum, and maximum) of TNA NF50 values
- Geometric mean titer (GMT) and corresponding 95% CIs for TNA NF50

Subject data listing with TNA assessments at baseline (prior to administration of ciprofloxacin or doxycycline on Day 1) and at Day 37 (2 weeks following the final dose of a two-dose vaccination series) will be presented.

The scatter plot of estimated GMTs and associated 95% CIs for TNA NF50 at Day 37 by treatment group will be provided. In addition, scatter plots of estimated GMTs and associated 95% CIs for TNA NF50 at Day 37 will be presented by each subgroup (age group and sex) in each treatment group.

## 7.2 Secondary Immunogenicity Endpoints

The secondary immunogenicity analysis is aimed to assess whether the immunogenicity of AV7909 two weeks following the final dose of a two-dose vaccination series is affected by concomitant dosing with oral ciprofloxacin or doxycycline.

Non-inferiority test will be constructed using the GMT ratio of TNA NF50 (Group 1/Group 3 or Group 2/Group 3) between IP group with participants that received both AV7909 and ciprofloxacin or doxycycline (Group 1 or 2) and the IP group with participants that received AV7909 only (Group 3). Point estimate and the 95% CI for the GMT ratio will be estimated using the linear regression based on log10 transformed TNA NF50 with equal variance. If the lower bound of the two-sided 95% CI of geometric mean ratio is greater than the non-inferiority margin of 0.5, it is concluded that the immune response in the group who received AV7909 plus either ciprofloxacin or doxycycline is non-inferior to the group which received AV7909 alone and thus that either ciprofloxacin or doxycycline did not demonstrably affect the immunogenicity of AV7909.

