10.5.2. Non-Inferiority Testing for Secondary Immunogenicity Endpoints

Two-sided 95% CIs will be calculated for the geometric mean ratio of TNA NF₅₀ values at Day 37 between the AV7909 + antibiotic group and the AV7909 only group (Group 1 vs. Group 3, Group 2 vs. Group 3). To conclude that ciprofloxacin or doxycycline does not reduce the immune response to AV7909, the lower bound of the 95% CI should be greater than the non-inferiority margin of 0.5.

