10.5.3. Exploratory Analysis for Immunogenicity

To evaluate the possible impact on the immunogenicity endpoints of a population not balanced by age and gender, exploratory analyses will be conducted using linear regression to compare the

AV7909 Anthrax Vaccine

IND 014451

Protocol EBS.AVA.210, Version 3.0 (28 October 2019)

immunogenicity response at Day 37 between each AV7909 + antibiotic group and the AV7909 only group, ie, between Group 1 (AV7909 + ciprofloxacin) and Group 3 (AV7909) and between Group 2 (AV7909 + doxycycline) and Group 3 (AV7909). In the linear regression models, the stratification factor, study site, will be included in the model as a random effect; participant sex and age will be included as fixed factors with age being dichotomized into ≤ 30 and >30 . The adjusted GMT ratios for the TNA NF₅₀ values will be provided with 95% CI.

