## 2.5 Randomization and Blinding

### 2.5.1 Randomization

At the Randomization visit (Day 1), after the PI has confirmed that the participant meets all the inclusion criteria and none of the exclusion criteria, a central randomization process will be used to assign each participant to one of the three open-label IP groups with the ratio of 1:1:1 (block size of 3). Approximately the first 40 participants who are randomized into IP Groups 1 and 2 will be assigned to Treatment Groups 1A or 2A while the remaining 30 participants randomized into IP Groups 1 and 2 thereafter will be assigned to Treatment Groups 1B or 2B.

Randomization will be stratified by site. The sites will be asked to the extent possible to execute a recruitment process that achieves a representative racial/ethnic distribution in populations that are reasonably gender- and age-balanced (i.e., at least 40% male with 40% of participants in the two age ranges of 18 to 30 years of age and 31 to 45 years of age).

A randomization plan will be prepared and finalized prior to randomization of the first participant. The specific instructions for randomizing participants will be provided in the Pharmacy Manual.

A screen failure is a participant from whom informed consent is obtained and documented in writing, but who is not subsequently randomized to study treatment. Reasons for screen failure are to be recorded on the electronic case report forms (eCRFs).

Participants who are screen failures are permitted to be rescreened one time (only) according to the PI's discretion. If a participant is rescreened, a new subject ID will be assigned. To link records to the same participant, the participant's previous subject ID will be recorded in the eCRF along with the new subject ID. Participants who complete the rescreening and are randomized in the study will not be considered as screen failures.

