## **4.6 Adjustment for Covariates**

An exploratory immunogenicity linear regression analysis will be conducted with adjustment for site, and covariates age and sex, as specified in [Section 7.2.1](#).

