### 7.2.1 Exploratory Analysis for Immunogenicity

To evaluate the possible impact of imbalance in sex and age on the immunogenicity endpoints, exploratory analyses will be conducted using linear regression to compare the immunogenicity response at Day 37 between each AV7909 + antibiotic group and the AV7909 only group, i.e., between Group 1 (AV7909 + ciprofloxacin) and Group 3 (AV7909) and between Group 2 (AV7909 + doxycycline) and Group 3 (AV7909). In the linear regression models, the stratification factor, study site, will be included in the model as a random effect; treatment group, participant sex and age will be included as fixed factors with age being dichotomized into ≤30 years and >30 years. The adjusted GMT ratio for TNA NF50 will be provided with 95% confidence interval. Any differences between the exploratory (adjusted) and the primary (unadjusted) analyses will be discussed in the final CSR.

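### The formal TNA non-inferiority regression leaves out site, the only stratification factor, so its confidence interval is wider than the design requires if titres differ by site

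*SAP*

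**What the plan says.** SAP 2.5.1 assigns participants centrally to "one of the three open-label IP groups with the ratio of 1:1:1 (block size of 3"), and states "Randomization will be stratified by site". No other stratification factor is named. Sex and age group are recruitment targets only.

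For the formal comparison of Group 1 or Group 2 with Group 3, SAP 7.2 states: "Point estimate and the 95% CI for the GMT ratio will be estimated using the linear regression based on" log10-transformed NF50 with equal variance. Non-inferiority is concluded if the lower bound of the two-sided 95% interval exceeds 0.5. No covariate is listed. Protocol 10.5.2 says only that "CIs will be calculated for the geometric mean ratio of TNA" NF50 and names no model.

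Site adjustment appears elsewhere. SAP 4.6: "An exploratory immunogenicity linear regression analysis will be conducted with adjustment for site, and covariates age and sex". Protocol 10.5.3: "In the linear regression models, the stratification factor, study site, will be included in the model as a random effect", alongside sex and dichotomised age. SAP 7.2.1 repeats that model and adds: "Any differences between the exploratory (adjusted) and the primary (unadjusted) analyses will be discussed in the final CSR". So the formal analysis is unadjusted by the SAP's own label.

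**The concern.** Blocking 1:1:1 within site balances the groups across sites, so differences in titre between sites largely cancel out of the group contrast. A model without site does not know this. It leaves the between-site variance in the residual and overstates the standard error of the contrast. If sites differ, the interval is then too wide and the one-sided error falls below the nominal 2.5%.

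At stake is precision in a pass/fail decision. A comparison whose observed ratio falls just short of the unadjusted threshold could miss the 0.5 margin only because the analysis ignored the way participants were randomised. The concern is limited to site. Leaving out sex and age group does not ignore the design.

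**Working it through.** **Inputs.** From SAP 2.4: 53 evaluable per group, CV 100%, true ratio 0.85, one-sided alpha 2.5%, and 70 planned per group with up to 25% loss. From SAP 7.2: margin 0.5. From SAP 3.3: about 4 sites. The site share of log-titre variance, ρ, is in neither document. It is assumed to be 0, 5, 10 or 20%.

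**The plan's own figure.** SAP 2.4 states: "This assumes that the true ratio of the geometric means between two groups is 0.85".
- SD of ln NF50 = √ln(1 + 1²) = √0.6931 = 0.8326
- Distance to the margin = ln(0.85/0.5) = 0.5306
- Standard error = 0.8326 × √(2/53) = 0.1617
- Power from the noncentral t with 104 df is 90.2% at 53 per group and 89.6% at 52

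The stated 53 per group reproduces, with no site term. The 100% CV is total within-group variability, so the stated power does not depend on adjusting.

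**Passing threshold.** The smallest observed ratio that passes is 0.5 × exp(t × SE).
- Unadjusted: 0.5 × exp(1.983 × 0.1617) = 0.5 × exp(0.3207) = 0.689
- Adjusted, balanced sites, 3 further df used: SE becomes 0.1617 × √(1 − ρ). At ρ = 10% this is 0.1534, and 0.5 × exp(1.984 × 0.1534) = 0.678

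**Simulation.** There were 200,000 trials per setting with 4 sites. Each trial had 70 per group balanced within site, with 17 per group removed at random to leave 53. Total log variance was held at ln 2. The unadjusted comparison of two groups was set against treatment plus fixed site.

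| Site share | Type I error, unadjusted | Type I error, adjusted | Power at 0.85, unadjusted | Power at 0.85, adjusted | CI width, adjusted/unadjusted | Smallest passing ratio, adjusted (by formula) |
|---|---|---|---|---|---|---|
| 0% | 2.55% | 2.56% | 90.1% | 89.9% | 1.004 | 0.689 |
| 5% | 2.28% | 2.48% | 90.6% | 91.3% | 0.978 | 0.684 |
| 10% | 2.01% | 2.49% | 91.0% | 92.7% | 0.952 | 0.678 |
| 20% | 1.68% | 2.51% | 92.0% | 95.3% | 0.897 | 0.666 |

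Monte Carlo standard errors are about 0.04 points for type I error and 0.07 points for power.

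**Cross-checks.** A separate simulation (8,000 trials per setting, even and uneven site sizes, 25% random exclusions) found the unadjusted interval about 2%, 5% and 12% wider than the adjusted one at 5%, 10% and 20%. That is the same comparison taken the other way round. Drawing the site effects at random gives a smaller mean narrowing, about 1.5%, 3.4% and 7.4%, in the same direction. With perfect balance and no exclusions, the unadjusted one-sided error is 2.2%, 1.9% and 1.4% by formula. Random exclusions therefore weaken the conservatism but do not remove it.

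**The case against.** The plan has not overlooked site. It prespecifies a site-adjusted ratio with a 95% interval and requires differences from the unadjusted result to be discussed in the study report. The formal test is valid, conservative and consistent with the sample-size calculation. The endpoint is secondary and is tested formally only if the corresponding PK endpoint is met. Site variance may also be small: one validated assay at one laboratory, healthy adults aged 18 to 45, baseline titre below the limit of detection, and a one-day sampling window in most groups. Finally, 53 per group is the worst case. With all 70 evaluable, unadjusted power is already about 96.3% with no site variance, and adjusting adds only about 0.3, 0.6 and 1.0 points at shares of 5%, 10% and 20%.

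Most of this stands, and it limits the size of the point. The gain may be nil, and at a share of 5% or less it is trivial. But the exploratory model does not answer the point. It cannot change the formal conclusion, and because it adds sex and age at the same time it does not isolate the effect of site. It also fits site as a random effect, although a variance component is poorly estimated from about 4 sites. That the unadjusted test is safe is no reason to leave out the one factor the randomisation was stratified on, when including it costs almost nothing.

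**Conclusion.** The concern holds as a modest loss of efficiency. The decision model omits the only stratification factor. If titres differ by site, the interval is too wide and the one-sided error is below 2.5%. At an assumed site share of 10%, adjusting narrows the interval by about 5%, adds 1.7 points of power (92.7% against 91.0%), and moves the passing ratio from 0.689 to 0.678. At 0% it changes essentially nothing. False non-inferiority claims are not made more likely, and the stated 90% power is unaffected.

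These sizes rest on the assumed site shares, about 4 sites, pairwise comparisons at 53 per group, and exclusions unrelated to site or treatment.

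**What to change.** In SAP 7.2, before database lock, estimate the Group 1/Group 3 and Group 2/Group 3 GMT ratios and their 95% intervals from a linear model of log10 NF50. Use treatment group and study site as fixed effects, with equal variance. Base the 0.5-margin decision on that model and report the unadjusted analysis as a sensitivity analysis. Add a sentence on how a site with no evaluable participants in one group will be handled. Sex and age group can stay in the exploratory model of SAP 7.2.1. Record the departure from Protocol 10.5.3, which uses site only in the exploratory model. Protocol 10.5.2 names no model for the formal interval and does not stand in the way.

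The cost is SAP wording. Site is already recorded, and a model containing it is already to be programmed. The change uses 3 degrees of freedom with 4 sites, or 4 with the five sites the protocol allows. If site explains nothing, the interval is about 0.4% wider and power about 0.2 points lower.
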